4.2 Handling of dropouts or missing data

4.2.1 Handling of missing data for efficacy analysis

Calculation of derived efficacy variables in the presence of missing data is described in individual sub-sections of [Section 8.1](#). All derived efficacy variables will be calculated using observed data, and any resulting missing data will be handled as described in this section. All non-responder imputation (NRI) and multiple imputation (MI) as described below will be performed only for subjects in the FAS for AS0009.

For assessments missing during AS0008 which are used in AS0009 for reporting maintenance of response, the imputed value (based on NRI) from the AS0008 database will be used.

For all visits in AS0009 (including AS0009 EV), missing values or values which cannot be constructed due to missing components for binary secondary/other efficacy variables (ASAS40, ASAS20, ASAS5/6) will be imputed using NRI. For each visit, subjects with missing data or who have dropped out of the study will be counted as non-responders. This includes any subjects with missing baseline values.

For missing continuous secondary/other efficacy variables an MI approach will be used. This will be performed for the following variables/endpoints:

- ASAS components:
 - Total Spinal Pain, Question 1 from TNSP
 - Inflammation, derived as the mean of Question 5 and 6 from the BASDAI
- ASDAS-CRP components:

- Total Back Pain, Question 2 from the BASDAI
- Duration of Morning Stiffness, Question 6 from the BASDAI
- PGADA (this is already included below as this is required as a standalone endpoint)
- Peripheral Pain/Swelling, Question 3 from the BASDAI
- CRP

ASDAS-CRP and ASDAS-ID will be determined after MI of the individual components of the ASDAS-CRP (ie, MI will not be applied to the overall ASDAS-CRP score). Note that for CRP the rules for handling measurements that are below the limit of quantification (BLQ) should be followed as per [Section 8.1.2](#). Thus, if any imputed values are <2mg/L these will be replaced with a constant value of 2mg/L for subsequent derivation of ASDAS-CRP. For the ASDAS-ID, the number of subjects within each disease activity category will be derived for each imputation and the mean number of subjects within each category across imputations will be presented.

- BASDAI
- BASFI
- BASMI
- MASES

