 - For MASES the MI model will be restricted to subjects with a MASES score > 0 at AS0008 Baseline. Subjects with a MASES score of zero at AS0008 Baseline will be excluded prior to performing the procedure outlined below.
- PGADA
- TNSP
- SF-36
 - For SF-36 this will be performed for the Physical Component Summary score (PCS) and Mental Component Summary score (MCS) and for each of the 8 domain scores (Physical Functioning, Role Physical, General Health, Bodily Pain, Vitality, Social Functioning, Role Emotional and Mental Health).
- ASQoL
- HADS-A and HADS-D
 - Incidence of normal HADS-A and HADS-D scores (defined as having HADS-D<8 and HADS-A<8 at the same visit) will be derived at each visit using the values for HADS-A and HADS-D obtained after MI
- CRP
 - Note that for CRP as a standalone endpoint the rules for handling measurements that are below the limit of quantification should be followed as per [Section 8.1.12](#). Thus, if any

imputed values are <0.16mg/L these will be replaced with 0.08mg/L prior to any subsequent reporting.

The missing absolute value (not the change from baseline) will be replaced by one of a set of plausible values, where each value is a Bayesian draw from the conditional distribution of the missing data given the observed data. The basic assumption in MI is that the underlying missing data mechanism is ignorable, e.g. the missing data are missing at random.

All MI procedures will be performed using data from both AS0008 and AS0009 such that missing data across both studies will be imputed. Any previous MI or last observation carried forward (LOCF) (or other e.g., next observation carried backward) imputation performed in AS0008 will not be considered for AS0009 such that the procedure will use OC data only across both studies.

As the AS0008 Week 48 time point is synonymous with the AS0009 EV time point, this will be incorporated once only into the model.

The SAS® PROC MI procedure will be used for the imputation.

The MI consists of 3 steps:

- The missing data are imputed m times to create m complete datasets.
- The m datasets are summarized.
- The results of the m summaries are combined into a single result.

The MI method will be applied as follows:

Step 1

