- Create a data set, sorted by treatment group at completion of AS0008, of subjects with observed values and missing values needing imputation. Missing values will be separated into non-monotone (ie, intermittent missing values between completed assessments) and monotone (ie, missing values after the subject dropped out). The procedure will sequentially estimate an imputation model for the efficacy variable at each post-AS0008 Baseline visit where efficacy variables are collected, with AS0008 Baseline, geographic region, and past TNF inhibitor exposure (as collected on the eCRF in AS0008 for past anti-TNF exposure) as covariates, separately for each treatment group at the completion of AS0008.
- Intermittent missing data will be imputed by draws from the imputation model using the Markov-Chain Monte Carlo (MCMC) method with multiple chains and monotone imputing. A total number of imputations will be 100. The seed used for these imputations will be 2017.

Note: All MI procedures described in this SAP will use the same seed.

- The post-AS0008 Baseline values will be specified in chronological order in the imputation model so that the SAS® PROC MI imputes variables from left to right. In case an AS0008 Baseline raw value is missing, the study participant will be excluded. The imputation model based on the MCMC method will only allow multivariate normal continuous variables as predictors. Therefore, past TNF inhibitor exposure and geographic region will be re-coded as indicator variables. For past TNF inhibitor exposure, this will be 0 for no past exposure and 1 for past TNF exposure. For region, there will be 2 indicator variables, the first of which will

be 1 for subjects from Western Europe and 0 for all other subjects and the second of which will be 1 for subjects from Eastern Europe and 0 for all other subjects. The order of the covariates in the model will be as follows: region indicator variables (Western Europe =1, Other =0; Eastern Europe=1, Other=0), past TNF inhibitor exposure (Yes=1, No=0), Baseline and then the visit variables.

- Once the intermittent missing data are imputed, the monotone missing data will be imputed including covariates as defined above, based on the datasets created by the intermittent missing data MI. Since this dataset already has 100 imputed values at each visit, only 1 imputation will be performed.

Step 2

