^b For the purposes of the MI any numerical CRP values obtained in AS0009 that were <0.16mg/L will be substituted with half the lower limit of quantification (LLOQ) from AS0008 (ie, 0.08mg/L) prior to performing the MI. Subsequently any observed or imputed values of <2mg/L will be replaced by the value of 2mg/L for the purposes of deriving the ASDAS-CRP. Any CRP values of >=500mg/L will be set to missing prior to performing the MI procedure.

^c For the purposes of the MI any numerical CRP values obtained in AS0009 that were <0.16mg/L will be substituted with half the LLOQ from AS0008 (ie, 0.08mg/L) prior to performing the MI. Subsequently any imputed values of <0.16mg/L will be replaced by the value of 0.08mg/L for the purpose of summaries based on imputed data. Listings will display the original result. CRP values of >=500mg/L will be set to missing prior to performing the MI procedure; the subsequently imputed CRP value will be included in the summary tables.

Step 3 (Excluding CRP)

The 100 imputed datasets will be combined, and simple means and standard errors will be calculated using Rubin’s rules (via SAS® PROC MIANALYZE). For calculation of other

descriptive statistics (median, Q1, Q3, minimum and maximum), Rubin's rules do not apply. Multiple imputation estimates will be computed by calculating arithmetic means of the estimates from the multiple repetitions of the imputation algorithm. Thus, for median, Q1, Q3, minimum and maximum the following approach will apply:

- The data will be summarized by treatment, visit and imputation and the summary statistics will be computed.
- Results will be summarized by taking the mean value of each summary statistic at each visit across all imputations.

The number of decimal places will remain the same as the original for display purposes (ie, if the mean was presented to 1 decimal place, the mean of the means will also be presented to 1 decimal place).

Step 3 (CRP only)

The CRP data will be presented using the geometric mean, 95% confidence interval (CI) for the geometric mean, median, Q1, Q3, minimum and maximum. The change from Baseline will be expressed as the ratio to Baseline in the summaries. The following approach will be applied:

- Following the MI procedure the ratio to Baseline will be calculated for any of the imputed values
- The natural logarithm of the absolute values and of the ratios to Baseline will be calculated
- The logged values will be summarized by treatment, visit and imputation

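### Missing CRP is imputed untransformed under a normal model, low draws are set to 0.08 mg/L and only then logged, which biases the CRP geometric means and ratios to Baseline downwards and widens their intervals

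*SAP*

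**What the plan says.** SAP 4.2.1 gives one procedure for all continuous efficacy variables, including CRP as a standalone endpoint and CRP as a component of ASDAS-CRP. "The missing absolute value (not the change from baseline) will be replaced by one of a set of plausible values". Intermittent gaps are filled by MCMC in SAS PROC MI. On that model the SAP says: "The imputation model based on the MCMC method will only allow multivariate normal continuous variables as predictors". After dropout, "the monotone missing data will be imputed including covariates as defined above". The number of imputations is 100. No transformation of CRP before imputation is mentioned.

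Limits in mg/L are then applied to the draws. For standalone CRP, Table 4-1 footnote c says that "any imputed values of <0.16mg/L will be replaced by the value of 0.08mg/L for the purpose of summaries based on imputed data", and the body text repeats the rule. For ASDAS-CRP, "if any imputed values are <2mg/L these will be replaced with a constant value of 2mg/L". Imputed CRP has no upper limit.

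Step 3 (CRP only) comes after the imputation. Ratios to Baseline are formed, then "The natural logarithm of the absolute values and of the ratios to Baseline will be calculated". The logged values are pooled by Rubin's rules and back-transformed to a geometric mean with a 95% confidence interval.

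Table 4-2 lists multiple imputation as the only method for CRP, ASDAS-CRP and ASDAS-ID. SAP 8.3 limits the additional observed-case summaries to ASAS40, ASAS20, ASAS5/6 and BASDAI.

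**The concern.** The imputation model and the analysis use different scales. By choosing geometric means and ratios for CRP alone among the imputed endpoints, and by treating values of 500 mg/L or more as extreme outliers (SAP 8.1.12), the SAP accepts that CRP is right-skewed. Amendment 1 moved the presentation of CRP to geometric means but records no matching change to the imputation scale.

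A normal distribution with the mean and SD of a skewed, near-zero variable has a large share of its mass close to or below zero. On a bounded 0 to 10 score, clipping such draws at the limit is mild. Here the clipped draws become 0.08 mg/L and are then logged. Against an assumed geometric mean of 3 mg/L, each lies ln(3/0.08) = ln(37.5) = 3.62 log units below the centre.

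The result would be an overstated CRP reduction and a distorted interval, with an error that grows as missing data accumulate over four years. SAP 5.1.1 notes that CRP is also missing at every missed or remote COVID-19 visit. SAP 8.5 plans no COVID-19 efficacy sensitivity analysis, and no other planned summary would reveal the problem.

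**Working it through.** The documents give no CRP figure for this point, so there is nothing to reproduce. From the documents: up to 285 subjects, hence about 140 in each AS0008-completion group if evenly split; 100 imputations; the 0.16/0.08 and 2 mg/L rules; the order of steps. Assumed: lognormal CRP, Baseline geometric mean (GM) 10 or 15 mg/L, later GM 2 to 5 mg/L, log-SD 0.8 to 1.4, log-scale correlation between visits 0.4 to 0.8, and 10% to 30% missing at the last visit.

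**Step 1: a single normal draw.** Match a normal to a lognormal with GM 3 and log-SD 1.0.

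- Mean = 3 × exp(1.0²/2) = 4.95; SD = 4.95 × √(exp(1.0²) − 1) = 6.48.
- Share of draws below 0.16 = Φ((0.16 − 4.95)/6.48) = Φ(−0.74) = 0.23.
- Share of true values below 0.16 = Φ(ln(0.16/3)/1.0) = Φ(−2.93) = 0.0017.
- With those draws set to 0.08 and logged, the GM of the imputed values is 2.12 instead of 3.00, and their log-SD is 1.95 instead of 1.0.

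Over GM 2 to 5 and log-SD 0.8 to 1.4, 15% to 35% of draws fall below 0.16 (true values: 0% to 3.6%), and the GM of the imputed values is 12% to 38% too low.

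**Step 2: effect on the group.** The bias on the log scale is roughly the missing share times the log error in imputed subjects. At 20% missing: 0.20 × ln(2.12/3.00) = 0.20 × (−0.347) = −0.069, or about 7% too low. An observed Baseline is common to both, so the ratio to Baseline carries the same relative error.

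**Step 3: the full sequence.** Simulation used n = 140, Baseline plus four visits, monotone missing-at-random dropout, sequential Bayesian normal regression on three indicators, Baseline and earlier visits, 100 imputations, the 0.16/0.08 rule, logs, Rubin's rules and back-transformation, with 100 replicates in each of 13 scenarios. The same code was run with imputation on the log scale. Three of the scenarios (later GM 3, correlation 0.6):

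| Log-SD | Missing | Draws set to 0.08 | GM: SAP / log-scale / complete | Ratio: SAP / log-scale / complete | GM upper/lower limit: SAP / log-scale |
|---|---|---|---|---|---|
| 0.8 | 10% | 11% | 2.92 / 2.99 / 2.99 | 0.293 / 0.299 / 0.300 | 1.38 / 1.32 |
| 1.1 | 20% | 19% | 2.83 / 3.01 / 3.03 | 0.284 / 0.302 / 0.304 | 1.66 / 1.48 |
| 1.4 | 30% | 24% | 2.73 / 2.96 / 3.00 | 0.269 / 0.293 / 0.296 | 1.98 / 1.69 |

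Across all 13 scenarios, 10% to 26% of imputed values were set to 0.08. The GM and ratio were 2% to 3% low at 10% missing, 4% to 7% at 20% and 7% to 9% at 30%. Log-scale imputation stayed within about 1%. In the middle row the interval is ln(1.66)/ln(1.48) = 0.507/0.392 = 1.29 times as wide on the log scale; the range over scenarios is about 1.12 to 1.5. Coverage was 92% to 100%.

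The observed-case GM was itself 2% to 12% low under this dropout, so raw-scale imputation recovers little of that loss. The observed-case ratio was within 1% of the complete data, so the error in the ratio comes from the imputation scale.

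**Step 4: other designs.** A simulation with n = 142, eight visits and dropout completely at random gave 18% to 30% of draws set to 0.08 and an overall GM up to 9% low. Further runs with n = 140 and monotone dropout gave 17% to 26%, a GM 2.6% to 10.3% low, and a log-scale SE about 1.2 to 1.5 times that of log-scale imputation.

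**Step 5: ASDAS-CRP.** The CRP term is 0.579 × ln(max(CRP, 2) + 1). In imputed subjects it shifted by about +0.05 to +0.15, against about 0 to +0.03 with log-scale imputation. The 2 mg/L floor hides the low draws, and what remains is a normal centred near 4.95 rather than a skewed distribution centred at 3. At 10% to 30% missing, the group mean moves by 0.10 × 0.05 = 0.005 to 0.30 × 0.15 = 0.045.

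**The case against.** The raw scale is inferred. The phrase about the absolute value contrasts value with change, the sentence on multivariate normality is there to explain the recoding of region and TNF exposure, and mg/L limits could in principle follow a back-transformation. That is fair, but the SAP names no transformation and places the logarithm after imputation. If log-scale imputation was intended, the text still needs to say so.

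The stakes are low. Standalone CRP is in neither the protocol's nor the SAP's list of efficacy variables and appears only as a descriptive summary in SAP 8.3. The primary variables are safety variables, the secondary ones (ASAS40, ASAS20, BASDAI) do not use CRP, ASAS5/6 is handled by nonresponder imputation, and no hypothesis test is planned. This stands and limits the weight of the point.

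The sizes are illustrative. The CRP distribution, correlation and missing rate are assumed, and log-scale imputation does well partly because the simulated data are lognormal. Most imputed values (70% or more) are not floored, the interval error is mainly widening, and the ASDAS shift is small at group level and points towards worse disease. All of this stands for the magnitude. The direction needs only right skew close to zero. Opposite errors in two outputs from one imputation model also mean that the method cannot be defended as conservative.

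Finally, a change is not free of drawbacks. SAP 4.3 has all outputs except the COVID-19 ones produced at the Week 108 interim, and Amendment 2 followed review of those results. A new model breaks comparability with the interim CRP tables. That affects how the change is introduced, not whether the present sequence is sound.

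**Conclusion.** The concern holds. As written, SAP 4.2.1 imputes CRP on a scale where the normal model does not fit, converts the resulting low draws to 0.08 mg/L, and logs them. Under the assumed lognormal CRP and 10% to 30% missing, the geometric mean and ratio to Baseline come out about 2% to 10% too low, which overstates the CRP reduction. Intervals are roughly 12% to 50% wider on the log scale than they need be. The CRP term of ASDAS-CRP is about 0.05 to 0.15 too high in imputed subjects. The effect on ASDAS-ID, which depends on a fixed cut-off of 1.3, was not quantified.

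Confidence is high for the mechanism and its direction, and lower for the size, which depends on the actual CRP distribution and missing share. MCMC gaps were not simulated separately. The point should be corrected, but it does not touch the primary or secondary conclusions.

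**What to change.** State in SAP 4.2.1 that CRP, including Baseline CRP, is log-transformed for both the MCMC and the monotone regression step, for example with the PROC MI TRANSFORM statement, and back-transformed afterwards. Keep the existing 0.08 mg/L substitution for observed values and the 500 mg/L rule before imputation, and apply the 0.16/0.08 rule to back-transformed draws. Use the same imputations for standalone CRP and for ASDAS-CRP, with the 2 mg/L floor applied only when ASDAS-CRP is derived.

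Add an observed-case row for CRP to Table 4-2 and SAP 8.3. It checks the ratio to Baseline in particular; the observed-case geometric mean can itself be affected by dropout.

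The cost is one or two SAP sentences, one programming statement, the extra table, and re-running and checking the CRP and ASDAS outputs. Because interim results have been reviewed, record the change and its reason in the SAP amendment, and show the interim-method CRP results alongside so that the difference is visible.

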4.2.2 Handling of missing data for adverse events

A complete date must be established to correctly identify the AE as treatment-emergent. For purposes of imputing missing components of partially reported start and stop dates for AEs, the algorithms listed below will be followed. Start and stop dates of AEs will be displayed as reported in the subject data listings (ie, no imputed values will be displayed in data listings).

Partial or missing start dates for events recorded during AS0008 (including those which were ongoing at the start of AS0009) will be imputed using the imputed start date from the AS0008 database.

Imputation of partial AE start dates for events reported in AS0009 only will follow the rules below (treatment switching rules refer to AS0008 only and data were used directly from the AS0008 database):

- If only the month and year of the AE start date are specified, and the month and year of the start date of study medication in AS0009 are not the same as the month and year of the AE start date, and the subject did not switch treatment during that month and year, then use the 1st of the month of the AE start date.
- If only the month and year of the AE start date are specified, and the month and year of the start date of study medication in AS0009 are not the same as the month and year of the AE start date, and the subject switched treatment during the month and year of the AE start date, then use the date of treatment switch.

- If only the month and year of the AE start date are specified, and the month and year of the start date of study medication in AS0009 are the same as the month and year of the AE start date, then use the start date of study medication in AS0009 (regardless of treatment switching). If this results in a start date after a known end date use the 1st of the month of the AE start date.
- If only the year of the AE start date is specified, and the year of the start date of study medication in AS0009 is not the same as the year of the AE start date, and the subject did not switch treatment during the year of the AE start date, then use the 1st of January of the year of the AE start date.
- If only the year of the AE start date is specified, and the year of the start date of study medication in AS0009 is not the same as the year of the AE start date, and the subject switched treatment during the year of the AE start date, then use the date of treatment switch.
- If only the year of the AE start date is specified, and the year of the start date of study medication in AS0009 is the same as the year of the AE start date, then use the start date of study medication in AS0009 (regardless of treatment switching). If this results in a start date after a known end date use the 1st of January of the year of the AE start date.
- If only the year and day of the AE start date are specified, and the year of the start date of study medication in AS0009 is not the same as the year of the AE start date, then use January of the year of the AE start date together with the known day.
- If only the year and day of the AE start date are specified, and the year of the start date of study medication in AS0009 is the same as the year of the AE start date, then use the start month of study medication in AS0009 together with the known day.
 - If this results in a start date after a known end date use January of the year of the AE start date together with the known day.
 - If this results in a start date prior to the start date of study medication in AS0009 (in the imputed month) the event will be considered to be treatment-emergent.
- If the AE start date is completely unknown and the AE stop date is unknown or not prior to the start date of study medication in AS0009, then use the start date of study medication in AS0009.

Imputation of partial AE stop date:

- If only the month and year are specified, then use the last day of the month.
- If only the day and year are specified, then use December of that year
- If only the year is specified, then use December 31st of that year.
- If the stop date is completely unknown, do not impute the stop date.

In the event of ambiguity or incomplete data which makes it impossible to determine whether the AE was treatment-emergent, the AE will be considered treatment-emergent. For subjects who may have died during the study, imputed dates will be truncated at the date of death.

If the intensity of an AE is unknown, it is considered as severe. If the relationship to study drug is missing, it is considered as related.

If the seriousness of an AE is unknown, no imputation will be performed. Such events will therefore be excluded from any listings or summaries of SAEs. If the seriousness of an AE is unknown, every attempt should be made to resolve this prior to database lock.

